8.2 Serious and Unexpected Adverse Events

A serious adverse event is one which:

• is fatal or life threatening,

- is permanently or significantly disabling, or
- requires in-patient hospitalization or prolongation of hospitalization

An unexpected adverse experience is one which:

- is not previously reported with the agents or procedures being undertaken, or
- is symptomatically and pathophysiologically related to a reported toxicity but differs because of greater severity or increased frequency.

Important medical events that may not result in death, be life-threatening, or require hospitalization may be considered an SAE when, based upon appropriate medical judgment, they may jeopardize the subject and may require medical or surgical intervention to prevent one of the outcomes listed in the above definition.

The Investigator must report all SAEs and all deaths to the study sponsor or designee immediately by telephone and in writing within five (5) days. A toll free number and an SAE reporting form to report such events will be provided. See also section 11 with respect to administrative responsibilities.

9.0 STATISTICAL CONSIDERATIONS

9.1 Study Populations

The intent-to-treat population comprises all subjects who enroll in the study and who provide any post-screening data. The safety population comprises all subjects who receive any study treatment. For the purposes of this study the safety population will be used for efficacy and safety analyses.

9.2 Efficacy Analyses (Secondary Endpoints)

Efficacy endpoints are secondary analyses and include assessment of change in BCVA, mobility, contrast sensitivity, and visual fields.

BCVA will be measured with the electronic visual acuity testing algorithm (E-ETDRS) and will be assessed by comparison of the mean change in number of letters correct from baseline.

Mobility will be assessed by comparison of mean change in CIL from baseline, unilaterally and bilaterally.

Descriptive statistics will be used to tabulate and summarize study outcomes. The baseline results of clinical examinations of the injected eye serve as controls for the injected eye for the purpose of reporting changes in visual parameters from baseline to 6 or 12 months post-treatment. Results of testing of the non-tested eye will also be described. Continuous variables will be summarized descriptively (sample size, mean standard deviation and error,

minimum and maximum). Discrete variables will be summarized by frequency or percentage, and analyzed with non-parametric statistics.

Subjects who cannot perform a specific visual test at baseline will be assigned the lower limit of detection, if applicable, for the relevant test. Subjects with missing data (no assessment) at baseline will be considered non-evaluable for analysis of that assessment.

9.3 Safety Analyses

Adverse events will be monitored by the investigator and the subject. The safety analyses of AEs and laboratory parameters will include descriptive statistics by treatment group. Summaries of AEs will be generated, type (AE or SAE), body system and preferred term, severity, and relationship to study product.

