A group of 25-30 subjects who have participated in a prior jCell study will be eligible. A minimum of 18 months must have elapsed between the prior jCell treatment and treatment in this study and the subject must have completed the 12 month follow up visit from the prior study with a reasonable record of study compliance.

Study subjects will be screened for eligibility, informed consent obtained, and eligible subjects will receive a jCell injection in a previously treated eye of 6×10^6 jCell. Subjects who have previously had both eyes treated will only have one eye retreated, preferably the eye with best visual acuity. Exceptions to this can be made by the study investigator taking into consideration medical conditions or other circumstances that may impact the choice of eyes for treatment. Subjects will be monitored closely following injection for 60 minutes prior to being released home on the day of treatment, based on intraocular pressure <30mm Hg and vital signs returned to pre-injection. Following treatment, all subjects will be treated with ophthalmic corticosteroid eye drops to minimize any inflammation from injection for a minimum of 7 days (including tapering schedule), or longer as if determined by the study investigator. Blood samples for antibody testing (PRA and DRA) will be collected at baseline and at months 1 and 6. Subjects will be followed at specified intervals for 12 months for evidence of safety and efficacy.

Subjects may be asked to undergo additional, optional testing at baseline and specified timepoints to explore retinal sensitivity and the characteristics of the injected jCells during follow-up.

Number of patients:

25-30 (depending upon availability) previously treated jCell subjects will be retreated in one previously treated eye to assess safety of reinjection. If a subject has been previously treated with jCell in both eyes, the better seeing eye will be selected for re-treatment unless there are specific circumstances that make this not advisable, as judged by the study investigator. This is considered to be an adequate number of subjects to be able to judge whether the safety profile is consistent with that which has been seen previously with an initial treatment (JC-01 and JC-02) or a fellow eye treatment (JC-01E). This number assumes that there will be at least 25 previously treated subjects who desire a repeat treatment in a previously treated eye.

Diagnosis and main criteria for inclusion:

Inclusion Criteria

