3.2.2 Safety Endpoints

The main criteria that will be used to assess safety include:

- Incidence and severity of treatment-emergent adverse events (TEAE)
- Safety visual assessments: slit lamp and fundus exam, IOP

Blood samples will be collected from subjects at baseline and at designated times post-treatment to assess immunogenicity of the injected cells (PRA, DRA).

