7.1.4 Blood Samples for Antibody Testing

Blood samples will be collected for testing for Panel Reactive Antibodies (PRA) and Donor Reactive Antibodies (DRA) from subjects prior to treatment, at 4 weeks post-treatment, and at 6 months post-treatment. Details of preparation/shipping of samples will be provided separately.

7.1.5 **Ophthalmic AEs**

Procedures will be performed at scheduled intervals to specifically assess eye AEs that may not be detected by usual AE reporting and to try and visualize the injected cells. Please refer to the study procedure manual for details of all ophthalmologic assessment procedures.

Slit lamp and fundus exam - The binocular slit-lamp examination provides a stereoscopic magnified view of the eye structures in detail, enabling anatomical diagnoses to be made for a variety of eye conditions. This assessment will include detection of anterior chamber cell or flare; acute cataract development or progression in phakic patients, or vitreous haze. Fundus exam allows for inspection of the retina, the cellular graft, and detection of retinal detachment.

Optos photography - Optos photography includes a widefield dilated Optos photograph of the posterior segment with any cell cluster from the anterior vitreous visualized in the photo frame along with the posterior segment/fundus.

IOP - Intraocular pressure is measured with a tonometer as part of a comprehensive eye examination. Measured values of intraocular pressure are influenced by corneal thickness and rigidity

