5. DETERMINATION OF SAMPLE SIZE

25-30 (depending upon availability) previously treated jCell subjects will be re-treated in one previously treated eye to assess safety of reinjection. If a subject has been previously treated with jCell in both eyes, the better seeing eye will be selected for re-treatment unless there are specific circumstances that make this not advisable, as judged by the study investigator. This is considered to be an adequate number of subjects to be able to judge whether the safety profile is consistent with that which has been seen previously with an initial treatment (received in protocols JC-01 and JC-02) or a fellow eye treatment (received in protocol JC-01E). This number assumes that there will be at least 25 previously treated subjects who desire a repeat treatment in a previously treated eye.

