13.2 Adverse Events

All AE summaries will be restricted to treatment-emergent AEs (TEAEs), which are defined as those AEs that occurred after dosing and those existing AEs that worsened during the study. In the case of worsening in severity, a new entry is created in the database with start date equal to start of worsening. If it cannot be determined whether the AE is treatment-emergent due to a partial onset date, then it will be counted as such. Verbatim terms in the eCRFs will be mapped to SOCs and PTs using MedDRA, version 23.1.

AE summaries that are displayed by SOC and PTs will be ordered by descending subject count by SOC and PT within SOC. Summaries of the following types will be presented:

- Overall summary of TEAEs that contains a summary of the following:
 - Subject and event count of any TEAE
 - Subject and event count of TEAEs related to study drug
 - Subject and event count of serious TEAEs
 - Subject and event count of any serious TEAE related to study drug
 - Subject and event count of severe TEAEs related to study drug

Separate TEAE summary tables will be provided as follows:

- Subject incidence and event count of TEAEs by MedDRA SOC and PT.
- Subject incidence and event count of TEAEs by MedDRA SOC, PT, and highest severity. At each level of subject summarization, a subject is classified according to the highest severity if the subject reported more than one of the same event. Categories of severity will be "Mild", "Moderate", "Severe" and "Life threatening". Adverse events with missing severity will be assigned to "Severe" for this summary.
- Subject incidence and event count of TEAEs related to study drug by MedDRA SOC and PT. Related AEs are those reported as "Related" and "Possibly Related". At each level of subject summarization, a subject is classified according to the closest relationship if the subject reported more than one of the same event. Adverse events with a missing relationship will be considered related for this summary.
- Subject incidence and event count of serious TEAEs by MedDRA SOC and PT.

Separate listings of related TEAEs and SAEs will be provided.

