APPENDIX B: LIST OF TABLES, LISTINGS, AND FIGURES

jCyte, Inc Protocol No. JC02-2

The following proposal for Sections 14 and 16.2 is completed according to ICH E3 guidelines. The heading numbers and description are in **bold**. Minor changes from this planned index do not need to be amended in the statistical analysis plan.

Index of Section 14

14.3.1.1	14.3.1	14.3	14.2.4.2	14.2.4.1	14.2.3.2	14.2.3.1	14.2.2.2	14.2.2.1	14.2.1.2	14.2.1.1	14.2	14.1.5.1	14.1.5		14.1.4	14.1.3	14.1.2	14.1.1	14.1	14	Table Number
Study Drug Administration	Extent of Exposure	Safety Data	Contrast Sensitivity Test (CST): Non-Study Eye	Contrast Sensitivity Test (CST): Study Eye	Kinetic Visual Fields (KVF): Non-Study Eye	Kinetic Visual Fields (KVF): Study Eye	Low Luminance Mobility Test (LLMT): Both Eyes	Low Luminance Mobility Test (LLMT): Study Eye	Best Corrected Visual Acuity (E-ETDRS), Average Number of Letters Correct by Visit: Non-Study Eye	Best Corrected Visual Acuity (E-ETDRS), Average Number of Letters Correct by Visit: Study Eye	Efficacy Data	Concomitant Medications	Therapies	Prior and Concomitant Medications. Treatments and	Ocular Medical History	Medical History	Demographic and Baseline Characteristics	Subject Disposition	Demographic Data	Tables and Figures Referred to but not Included in the Text	Table Title
Safety Population			Safety Population	Safety Population	Safety Population	Safety Population	Safety Population	Safety Population	Safety Population	Safety Population		Safety Population			Safety Population	Safety Population	Safety Population	All Subjects			Analysis Set
																					Comment

CONFIDENTIAL

Page 26/32

S
<
 
0
H

jCyte, Inc Protocol No. JC02-2

Statistical Analysis Plan 09 Nov 2022

Table Number	Table Title	Analysis Set	Comment
14.3.2	Displays of Adverse Events		
14.3.2.1	Overall Summary of TEAEs	Safety Population	
14.3.2.2	TEAEs by System Organ Class and Preferred Term	Safety Population	
14.3.2.3	TEAEs by System Organ Class, Preferred Term and Maximum Severity	Safety Population	
14.3.2.4	Related TEAEs by System Organ Class and Preferred Term	Safety Population	
14.3.2.5	Serious TEAEs by System Organ Class and Preferred Term	Safety Population	
14.3.3	Ophthalmic Safety Examinations		
14.3.3.1	Slit Lamp Exam: Study Eye	Safety Population	
14.3.3.2	Slit Lamp Exam: Non-Study Eye	Safety Population	
14.3.3.3	Dilated Funduscopic Exam: Study Eye	Safety Population	
14.3.3.4	Dilated Funduscopic Exam: Non-Study Eye	Safety Population	

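### No planned table gives the proportion of re-injected subjects with any intraocular inflammation over 12 months; adverse event tables stop at SOC and preferred term, and the eye examination tables are per visit

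*Protocol*

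**What the plan says.** Protocol 3.2.2 makes the incidence and severity of treatment-emergent adverse events the first safety criterion. Protocol 9.3 describes the analysis: "Summaries of AEs will be generated, type (AE or SAE), body system and preferred term, severity, and relationship to study product".

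SAP 13.2 gives an overall count of subjects and events, and then "Subject incidence and event count of TEAEs by MedDRA SOC and PT", with further tables for highest severity, related events and serious events. The Appendix B index matches, for example "TEAEs by System Organ Class, Preferred Term and Maximum Severity" (Table 14.3.2.3). Neither document defines an adverse event of special interest, a grouped term or a MedDRA query.

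Outside the adverse event tables, Protocol 7.1.5 says of the slit-lamp examination: "This assessment will include detection of anterior chamber cell or flare; acute cataract development or progression in phakic patients, or vitreous haze". SAP 13.3 tabulates several eye findings by time point.

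On purpose and size, SAP 5 says that 25-30 subjects are enough to "judge whether the safety profile is consistent with that which has been seen previously with an initial treatment" or a fellow-eye treatment.

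**The concern.** Intraocular inflammation is one clinical entity that sites can record under several verbatim terms, for example iritis, uveitis, flare, vitritis or vitreous haze. A SOC-by-PT table separates these into rows. The SOC row above them merges them with every other eye event, such as injection-site bleeding or cataract. Neither row answers the simple question of how many re-injected subjects had any inflammation.

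The documents themselves make this a natural question. Protocol 1.3 states that nobody had yet been injected twice in the same eye. Protocol 1.1.3 says that allogeneic grafts in privileged sites can still be rejected. Protocol 5.3 gives all subjects steroid drops to limit inflammation. A judgement that re-injection looks like a first injection needs one incidence per hazard. At this sample size, rows of one or two subjects can look unremarkable when the combined count is not.

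**Working it through.** **1. Is there a figure to reproduce?** No. The sample size of 25-30 rests on availability and judgement. No expected rate, margin or precision is stated. The check is therefore of what the planned outputs contain, followed by an illustration with assumed inputs.

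**2. What each planned output gives**

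| Output | Content | Subjects with any inflammation over 12 months? |
|---|---|---|
| Table 14.3.2.1 | Overall, related, serious and severe related TEAEs | No |
| Tables 14.3.2.2 to 14.3.2.5 | SOC/PT, with severity, related and serious versions | No, terms are not grouped |
| SAP 13.3.1.1 | Flare grade, cataract type and grade, by time point | No, per visit; anterior chamber cell not listed |
| SAP 13.3.1.2 | Optic nerve, vitreous, macula, peripheral retina: normal, abnormal NCS or CS | No, per visit and not specific to inflammation |
| SAP 13.3.3 | IOP change | No |
| SAP 13.3.4 | Graft visibility and shape, including diffuse haze | No |
| SAP 13.3.5 | CME, epiretinal membrane, traction, EZ | No; OCT is scheduled only at Baseline and Month 12 or early termination |
| Listing 16.2.6.1 | All adverse events by subject | Only by hand count |

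Protocol Table 2 and section 6.3.2 schedule no slit-lamp or fundus examination at Day 7. Slit-lamp biomicroscopy at that visit is optional and exploratory, and SAP 11.2 puts it in listings only. Between Day 1 and Day 28, inflammation therefore reaches the summary tables mainly as adverse event terms. SAP 13.2 does not say that those tables are split by eye.

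**3. Can the count be recovered from the preferred-term rows?** Let row *j* contain *x_j* subjects and let *U* be the number of subjects with at least one of the terms. Then max(*x_j*) ≤ *U* ≤ min(*n*, Σ*x_j*). One subject can be in several rows, so the tables fix *U* only within these limits.

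**4. How large could the dilution be?** Assumed inputs: *n* = 28, true incidence *p* = 20%, *k* = 4 terms. Affected subjects are spread over the terms by multinomial simulation, and the largest row is E[max(*x_j*)]/*n*.

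| Coding assumption | Largest row, mean | Chance that some row reaches 4 subjects |
|---|---|---|
| One term each, equal spread | 9.5% | 19% |
| One term each, spread 60/20/10/10 | 12.6% | 46% |
| Two of the four terms each | 14.8% | 65% |
| Grouped count, for comparison | 20% | 84% |

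The last entry is exact: 1 − Σ C(28, *j*) 0.2^*j* 0.8^(28−*j*) over *j* = 0 to 3 = 0.84. In the two-term case the rows add to 2 × 20% = 40% on average, so adding rows overshoots while the largest row undershoots.

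Sensitivity with one term each, equal spread, 3-5 terms and *n* = 25-30: the largest row averages 6.9-8.8% at 15% incidence, 8.5-11.1% at 20%, and 11.5-15.4% at 30%.

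**5. What a grouped line would show.** Six of 28 subjects is 6/28 = 21.4% (exact 95% CI 8.3-41.0%). Split 2, 2, 1, 1 over four terms, the same subjects appear as rows of 2/28 = 7.1% and 1/28 = 3.6%. At the planned sizes, 5/25 = 20.0% (6.8-40.7%) and 6/30 = 20.0% (7.7-38.6%). With no cases, the two-sided 95% upper limit is 13.7% at 25 and 11.6% at 30.

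**The case against.** The strongest reply is that inflammation is not ignored. A reader of SAP 13.2 alone might infer that it goes unreported, and the documents do not support that. SAP 13.3 tabulates flare by grade and clinical significance, vitreous and retinal findings, cataract grade, IOP change and CME, in Tables 14.3.3.1 to 14.3.3.8. Nor are adverse events shown only by SOC and PT: severity, relatedness, seriousness and overall counts are planned too. This stands. What remains is that these are findings at visits or ungrouped event counts, not the proportion of subjects ever affected.

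A second reply is that the incidence is not lost. Adverse events are listed by subject, and with 25-30 subjects a hand count is easy. That is true, but SAP 6 would label a count made after lock post hoc and exploratory, and the terms would be chosen with the events in view.

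A third is that the illustration favours the concern. Equal spread over four terms gives more dilution than uneven spread, and one term per subject is a simplification. Relaxing either assumption raises the largest row, as shown above. If sites use one dominant term, the problem nearly vanishes.

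Finally, the comparison is with JC-01, JC-02 and JC-01E. The visible text does not show how their events were summarised, and if it was by SOC/PT, the planned tables are the like-for-like comparison. This limits what a grouped rate can be set against, but not its value in describing this study.

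**Conclusion.** The gap is real and concerns the primary objective: no planned table gives the subject-level incidence of intraocular inflammation over 12 months, and it cannot be derived from the preferred-term rows.

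Its size depends on inputs that the documents do not give. Under 20% incidence, four terms and 28 subjects, the largest row averages 9.5-14.8% across the three coding assumptions. The documents show that inflammation is anticipated. A reader might infer that it is the main hazard of re-injection, but the text available does not rank hazards, and the conclusion does not need that ranking. The study is descriptive, with no threshold attached to any event rate, so no formal decision changes. What changes is whether the primary safety result can be read directly, with its uncertainty. Some of the protocol background and the table shells were not available to check.

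**What to change.** In SAP 13.2, add one TEAE table by grouped term, with:

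- intraocular inflammation at least, and also raised IOP, cataract development or progression, and retinal detachment or tear;
- the list of preferred terms for each group fixed before database lock;
- each subject counted once per group, with an exact 95% confidence interval;
- worst severity and onset period (for example Day 0-7, Day 8-28, after Day 28);
- restriction to the study eye where laterality is recorded.

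Keep the SOC/PT tables. Add anterior chamber cell to the slit-lamp table in SAP 13.3.1.1 if it is recorded.

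The cost is one SAP paragraph, one term list and one table, with no new data. Appendix B already allows minor index changes without an amendment, but the term list should be written down and dated. There are two drawbacks. The list is a judgement and has to be settled in advance. Comparison with the earlier studies requires applying the same list to their data, where those are available. If the database is already locked, the table is still worth producing, labelled post hoc as SAP 6 requires.

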9.4 Other Analyses

Demographics: Background and demographic data will be summarized for all subjects.

Exploratory: Data from exploratory imaging and retinal sensitivity assessments will be summarized.

10.0 ADMINISTRATIVE CONSIDERATIONS

10.1 Adverse Experiences

All adverse experiences (AE) must be recorded and reported to the sponsor. Any serious and unexpected AE will be reported to the sponsor or designee immediately by telephone and subsequently in writing within five (5) days. The Investigator must also notify the institutional IRB/EC. A full report, including clear photocopies of hospital records, consultants' reports, autopsy findings where appropriate, and a summary of the outcome by the Investigator, including his opinion of study relationship or attribution, will be furnished to the study Sponsor or designee as soon as practicable. It is the sponsor's responsibility to notify the FDA, other regulatory agencies as appropriate, and all clinical sites in compliance with regulatory requirements.

10.2 Institutional Review

Prior to implementation of this study, the research protocol and the proposed subject consent form must be reviewed and approved by a properly constituted Institutional Review Committee operating under the Code of Federal Regulations (21CFR Part 56). A signed and dated statement that they have approved the protocol must be submitted to the sponsor prior to the start of the study. This committee must also approve all amendments to the protocol.

10.3 Informed Consent

Informed consent will be obtained via discussions with the subject, explaining the rationale and experimental nature of the system, the duration of the trial, alternate modes of treatment,

and prevalent adverse reactions that might occur. Each subject will receive a copy of the signed consent form.

At the time of the discussions relating to enrollment or at any time during participation in the protocol that new information becomes available relating to risks, adverse events, or toxicities, this information will be provided orally or in writing to all enrolled or prospective subject participants in a timely fashion. Documentation of communication will be provided to the local institutional review board.

